											Follow-Up)		
	Screening					Treatm	ent			Safety	GVHD ^a	Survival		
Visit Day (Range)	Day -28 to -1	D1	D7	D14	D21	D28/56/84/ 112/140/168	D180	D196+ (Q28D/Q8W) ^b	ЕОТ	Last Dose + 30 days	Q28D/ Q8W°	Q8W From EOT	Notes	
Visit Window			Ⅎ	± 3 day	ys		± ′	7 days		+ 5 days	±7 days	± 14 days		
FEV1% (from PFTs)	X	Xg				X*	X	X**	X	X	X**		*Day 168 FEV1% may be omitted. **Q8W starting at Day 196 up to 1 year (ie, Days 252, 308, and 364) then Q16 weeks. Day 196 may be omitted.	
Disease/malignancy relapse	X							X*					*As clinically indicated.	
LSS		Xh				X	X	X	X				Part 2 only.	
QOL-SF-36 v2		Xh				X*	X	X**	X				Part 2 only.	
EQ-5D-3L		X^h				X*	X	X**	X				* Day 168 may be omitted.	
PGIC						X*	X	X**	X				**Day 196 may be omitted.	
PGIS		Xh				X*	X	X**	X					
New cGVHD therapy data												X		
Survival assessment												X		
Laboratory assessments														
Hematology	X	X^h	X	X	X	X	X	Q28D	X	X				
Serum chemistry	X	X ^h	X	X	X	X	X*	Q28D	X	X	X*		*Total bilirubin, ALT, and ALP. Direct and indirect bilirubin also required for participants with elevated total bilirubin.	
Lipid panel	X	X^h	X	X	X	X		X	X	X				
Serum pregnancy testing	X								X					
Serum or urine pregnancy testing						X		X						
Hepatitis screening	X													
HIV screening	X													
PK sampling (Part 1 and Part 1 expansion)		X	X			X							D1/7/28 only (predose, 1, 2, 5 h) *Treatment Group D in Part 1 expansion does not require PK sampling.	

Table 4: Schedule of Activities (Continued)

											Follow-Up	l	
	Screening					Treatm	ent			Safety	GVHD ^a	Survival	
Visit Day (Range)	Day -28 to -1	D1	D 7	D14	D21	D28/56/84/ 112/140/168	D180	D196+ (Q28D/Q8W) ^b	ЕОТ	Last Dose + 30 days	Q28D/ Q8W°	Q8W From EOT	Notes
Visit Window			±	3 day	ys	± 7 days				+ 5 days	±7 days	± 14 days	
PK sampling (Part 2)		X	X			Х							Participant 1-70: D1/7/28 (predose, 1, 2, 5 h). Participant 71-246: D7/28 (predose only).

VV-CLIN-000629 CONFIDENTIAL

^a Only for participants who completed itacitinib/placebo taper after an initial response (CR or PR) or discontinue early for reasons other than cGVHD disease progression and with no requirement for new cGVHD therapy (for a maximum of 24 months from Day 1).

b Every 28 days (± 7 days) up to 1 year (D364) from Day 1 and then every8 weeks (± 7 days), with the exception of hematology and serum chemistry, which will be performed every 28 days during the entire treatment period.

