8.2.2. Chronic GVHD Response Assessment

Chronic GVHD organ scoring and the overall severity score 0 to 10 will be assessed on Day 1 (ie, baseline). Postbaseline response evaluations will be performed by the treating physician according to the detailed schedule in Table 4. At each postbaseline assessment, each organ must be assessed using the same criteria as for baseline, and response should be determined by comparing the current organ assessment with the baseline organ assessment on Day 1. A high level summary of organ-specific response assessment criteria as per NIH consensus guideline (Lee et al 2015, Appendix E) are listed in Table 18 and Table 19.

Table 18: Organ Assessments

Organ	Evaluation	Criteria
Skin	NIH Skin Score, considering %BSA involvement and sclerotic features	Change of Skin score
Eyes	NIH Eye score	Change of Eye score
Mouth	NIH Modified OMRS (sum of scores for erythema, lichenoid, and ulcers)	Change of OMRS
Esophagus	NIH Esophagus score	Change in Esophagus score
Upper GI	NIH Upper GI score	Change in Upper GI score
Lower GI	NIH Lower GI score	Change of Lower GI score
Liver	Lab results for ALT, ALP, and total bilirubin	Change in values of lab results
Lungs	NIH Lung score and FEV1% (in participants using a bronchodilator, the post-bronchodilator response should be used for response assessment)	Change in FEV1%
Joints and fascia	NIH Joint and Fascia score and P-ROM scores	Change of Joint and Fascia score and P-ROM scores

Table 19: Postbaseline Response Evaluations

Organ	Organ Specific Response				
Skin	CR/not involved	PR in at least	PR or CR in 1 or	Progression in	Organ-specific
Eyes		1 organ with baseline	more organ(s) with baseline	1 or more	response 'unchanged' for
Mouth		involvement	involvement	organ(s) with baseline	all organs (incl.
Esophagus		AND .	AND	involvement	no involvement)
Upper GI		no progression in any other	progression in 1 or more	OR new occurrence	
Lower GI		organ (ie, CR,	organs (incl.	in an organ with	
Liver		PR, unchanged,	new occurrence	no baseline	
Lungs		or no involvement)	in an organ with no baseline	involvement AND	
Joints and fascia			involvement)	no CR or PR in any other organ	
Overall Response	CR	PR	MR	PD	Unchanged

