10.4.1. Primary Analysis

10.4.1.1. Part 1 and Safety Run-In for Part 1 Expansion

The toxicity of itacitinib will be monitored continuously for each treatment group using the Bayesian approach of Thall et al (1995, 1996) as extended by Thall and Sung (1998). Dose-limiting toxicities are defined in Section 6.1.1.3.

Historical data on similar patients show a toxicity rate of 25%. The probability of toxicity for the historical data is modeled by beta distribution (Beta [25, 75]). The prior probability of toxicity for the experimental regimen is also modeled by beta distributions (Beta [0.5, 1.5]), which have the same means as the corresponding beta distributions for the historical data. Denoting the historical probability of toxicity rate by p(TOX,H), the following decision criteria will be applied:

Stop if Prob
$$\{p(TOX,H) + \delta TOX < p(TOX,E) | data \} > 0.95$$
, where $\delta TOX = 0$

Participants from each treatment group will be monitored according to the following nonbinding stopping boundaries for toxicity in Table 25. If a boundary is reached, the sponsor and external DMC will investigate and decide on the most appropriate action.

Table 25: Toxicity Stopping Boundaries

# Participants (Inclusive)	Number of DLTs Required to Stop (Inclusive)
1-2	No limit
3-4	3
5-6	4
7-9	5
10-11	6
12-14	7
15-17	8
18-19	9
20	9

10.4.1.2. Part 2

The primary endpoint is Month 6 response rate, defined as the proportion of participants demonstrating a CR or PR at Month 6 as per standard criteria (Lee et al 2015). The comparison of Month 6 response rate between treatment cohorts will be conducted once the last participant completes the Month 6 visit or withdraws from the study. A CMH test with normal approximation will be used. Summary statistics and 95% CI will be provided.

Participants who have missing data for the Month 6 response rate assessment will be considered as nonresponders.

For the interim analysis, the statistical assumptions are specified in Section 10.5.

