APPENDIX E. RESPONSE ASSESSMENT FOR CHRONIC GVHD (NIH CRITERIA)

Response will be assessed using NIH 2014 criteria (Lee et al 2015)

a) Response determination for cGVHD by organ at postbaseline assessment

(comparison versus baseline)

Organ	Complete Response	Partial Response	Progression
Skin	NIH Skin Score 0 after previous involvement	Decrease in NIH Skin Score by 1 or more points	Increase in NIH Skin Score by 1 or more points, except 0 to 1
Eyes	NIH Eye Score 0 after previous involvement	Decrease in NIH Eye Score by 1 or more points	Increase in NIH Eye Score by 1 or more points, except 0 to 1
Mouth	NIH Modified OMRS 0 after previous involvement	Decrease in NIH Modified OMRS of 2 or more points	Increase in NIH Modified OMRS of 2 or more points
Esophagus	NIH Esophagus Score 0 after previous involvement	Decrease in NIH Esophagus Score by 1 or more points	Increase in NIH Esophagus Score by 1 or more points, except 0 to 1
Upper GI	NIH Upper GI Score 0 after previous involvement	Decrease in NIH Upper GI Score by 1 or more points	Increase in NIH Upper GI Score by 1 or more points, except 0 to 1
Lower GI	NIH Lower GI Score 0 after previous involvement	Decrease in NIH Lower GI Score by 1 or more points	Increase in NIH Lower GI Score by 1 or more points, except from 0 to 1
Liver	Normal ALT, alkaline phosphatase, and Total bilirubin after previous elevation of 1 or more	Decrease by 50%	Increase by 2 × ULN
Lungs	Normal FEV1% after previous involvement If PFTs not available, NIH Lung Symptom Score 0 after previous involvement	Increase by 10% predicted absolute value of FEV1% If PFTs not available, decrease in NIH Lung Symptom Score by 1 or more points	 Decrease by 10% predicted absolute value of FEV1% If PFTs not available, increase in NIH Lung Symptom Score by 1 or more points, except 0 to 1
Joints and fascia	Both NIH Joint and Fascia Score 0 and P-ROM score 25 after previous involvement by at least 1 measure	Decrease in NIH Joint and Fascia Score by 1 or more points or increase in P-ROM score by 1 point for any site	Increase in NIH Joint and Fascia Score by 1 or more points or decrease in P-ROM score by 1 point for any site
Global	Clinician overall severity score 0	Clinician overall severity score decreases by 2 or more points on a 0-10 scale	Clinician overall severity score increases by 2 or more points on a 0-10 scale

Source: Adapted from Lee et al 2015.

b) Response assessment for chronic GVHD by organ at baseline and at each post-baseline visit

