7.3.4. Best Overall Response

Best overall response for each participant is defined as best response during the course of the study (best in the categories of CR or PR), including responses at unscheduled visits.

Participants without a BOR (ie, participants not achieving a response of either CR or PR) in the treatment phase will be considered as nonresponders for BOR in the responder analysis. Number and percentage of participants in each best response category will be tabulated by treatment group.

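### Appendix E's symptom fallback for the lung requires no baseline symptoms; read literally, it scores FEV1-only lung disease as a lung CR at visits without spirometry, in conflict with Section 8.2.2

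*Protocol*

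**What the plan says.** Protocol Appendix E gives two routes to a lung CR. The main one is "Normal FEV1% after previous involvement". The substitute is "If PFTs not available, NIH Lung Symptom Score 0 after previous involvement". The substitute rules for partial response and progression are worded as a fall or a rise in the symptom score; the CR rule asks only for a current score of 0.

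Protocol Section 8.2.2 says that "each organ must be assessed using the same criteria as for baseline" and that "response should be determined by comparing the current organ assessment with the baseline organ assessment on Day 1". Table 18 in the same section gives the lung criterion as "Change in FEV1" (percent predicted) and mentions no substitute. That section presents Tables 18 and 19 as a summary of the Appendix E criteria.

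Table 4 schedules a response assessment at Day 14, every 28 days from Day 28 to Day 168, at Day 180, every 28 days from Day 196 to Day 364, and every 8 weeks after that. FEV1% is not scheduled at Day 14. It may be left out at Day 168, and from Day 196 the note reads "Q8W starting at Day 196 up to 1 year (ie, Days 252, 308, and 364) then Q16 weeks. Day 196 may be omitted".

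SAP Section 7.3.4 defines best overall response as "best response during the course of the study (best in the categories of CR or PR), including responses at unscheduled visits".

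**The concern.** Lung involvement does not need symptoms. Appendix D scores FEV1 of 60-79% as lung score 1 and lets FEV1 decide where it disagrees with the symptom score. Inclusion criterion 2a accepts lung score 1 as moderate disease, so a participant with symptom-free, lung-only disease can be enrolled.

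For such a participant the substitute CR rule can be met by a symptom score that was already 0 on Day 1. The same lung would then be a CR at a visit without spirometry and unchanged at the next visit with it. If sites apply the rule this way, or apply it differently from one another, false responses enter every analysis that takes the first or best response at any visit.

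**Working it through.** The plan states no figure on this point, so the check is a visit count and one test case.

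**Visits without FEV1 (Table 4 and its footnotes)**
- Response visits through Day 364: Days 14, 28, 56, 84, 112, 140, 168, 180, 196, 224, 252, 280, 308, 336 and 364, which is 15.
- No FEV1 scheduled: Days 14, 224, 280 and 336, so 4/15 = 27%.
- FEV1 may also be omitted at Days 168 and 196, so at most 6/15 = 40%.
- After Day 364, response is assessed every 56 days and FEV1 every 112 days. Taking 36 months as Day 1096 (assumed), response visits run from Day 420 to Day 1092: (1096 − 364)/56 = 13.1, so 13. FEV1 visits: (1096 − 364)/112 = 6.5, so 6. That leaves 13 − 6 = 7 of 13 without FEV1 (54%).

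**Test case: Day 1 FEV1 70%, symptom score 0, hence lung score 1**

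| Visit | Data | Involvement by any measure counts | Same measure as Day 1 required |
|---|---|---|---|
| Day 14 | no FEV1, symptom score 0 | lung CR | 0 − 0 = 0, unchanged |
| Day 28 | FEV1 70% | 70 − 70 = 0, unchanged | unchanged |

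The first column follows from Appendix E read alone. The second follows from Section 8.2.2.

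**Where a false lung CR would go**
- *Time to response* (SAP 7.3.2) and the *start of duration of response* (SAP 7.3.3) use the first CR or PR, and no confirmation is stated. Duration of response ends at progression, new systemic therapy or death. A return to unchanged at Day 28 is none of these, so a Day 14 start would persist.
- *Best overall response* (SAP 7.3.4) takes the best visit, unscheduled visits included, and SAP Appendix A, Table 2.2.8.1, tabulates it by organ. One visit is enough.
- *Overall category* (protocol Table 19): an overall CR follows only if every other involved organ is also in CR, for example in lung-only disease. If the other organs are unchanged, the overall result would be PR, assuming an organ CR counts as at least an organ PR. If another organ progresses, PD requires that no other organ be in CR or PR, so a false lung CR turns PD into mixed response.
- *Response rates*: SAP 7.3.1 sets these at Days 90, 180 and 365. The nearest scheduled visits are Days 84, 180 and 364, and all three have FEV1.

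**The case against.** The strongest reply is that the fallback should not be read alone. Section 8.2.2 requires the baseline criteria and a comparison with Day 1, Table 18 names change in FEV1%, and the Appendix E table is itself headed as a comparison with baseline. The Appendix E form records a lung symptom score, so a like-for-like baseline exists, and 0 to 0 is no change. The joints and fascia row says expressly that involvement on either measure is enough; the lung row does not. Nor does any text say that a visit with no spirometry scheduled counts as one where it is unavailable.

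This stands to the extent that the CR is one reading and not a certainty. It does not remove the conflict. At Day 14 the FEV1 criterion cannot be applied, because no FEV1 is taken. The tables in Section 8.2.2 are only summaries of Appendix E, so a site may reasonably treat Appendix E as the operative rule. No text says what to record for the lung at such a visit.

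The second reply is that little is at stake. Time to response, duration of response and best overall response are descriptive in the Part 1 expansion, and the visit schedule is the same in every group, so no bias between groups is shown. That is fair. However, protocol Section 10.4.2.3 plans a log-rank comparison of duration of response in Part 2.

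**Conclusion.** The point holds as a conflict between Appendix E and Section 8.2.2 that the plan should settle. On the literal Appendix E reading, FEV1-only lung disease scores a lung CR with no change in the lung at 4 of 15 response visits through Day 364, up to 6 if the optional omissions are taken, and at about half of the visits after that. The exposed outputs are time to response, the start of duration of response, and best overall response, overall and by organ. Progression elsewhere can also be relabelled as mixed response.

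Three stronger conclusions that a reader might draw are not supported:
- *That every such participant becomes a lung CR at each of these visits.* This requires ignoring Section 8.2.2 and Table 18.
- *That the Part 2 primary endpoint or the key secondary endpoints are generally compromised.* Spirometry is scheduled at the visits that serve Months 3, 6 and 12, so the lung score there is exposed only if that test is missed. The rule that "Participants who have missing data for the Month 6 response rate assessment will be considered as nonresponders" (protocol Section 10.4.1.2), like its counterpart in SAP 7.3.1, addresses a missing response assessment. Neither says how one missing organ test is classified, so the fallback leaves a gap in that rule and does not plainly reverse it.
- *That the share of participants affected can be estimated.* The documents give neither the frequency of lung involvement nor the share of it that is symptom-free.

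**What to change.** State in protocol Appendix E and in SAP Section 7.3:
- The symptom fallback can give a lung CR only if the Day 1 lung symptom score was at least 1.
- Where baseline lung involvement was by FEV1% alone (Day 1 symptom score 0), a visit without FEV1 cannot yield a lung CR or PR, and the lung is recorded as unchanged/not evaluated. This includes a missed test at the Month 3, 6 or 12 assessment.

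The symptom fallback stays available to participants who had lung symptoms on Day 1, in keeping with the adopted criteria. Its progression rule already requires a rise in score and need not change.

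The cost is wording in two places and slightly fewer early and best responses. No tests or visits are added.

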APPENDIX F. PATIENT GLOBAL IMPRESSION OF CHANGE AND PATIENT GLOBAL IMPRESSION OF SEVERITY

Patient Global Impression of Change (PGIC)

Please choose the response below that best describes the overall change in your chronic graft versus host disease symptoms since you started taking the study medication . My chronic graft
versus host disease symptoms are:
☐ Very Much Better
Moderately Better
A Little Better
☐ No Change
A Little Worse
Moderately Worse
☐ Very Much Worse
Patient Global Impression of Severity (PGIS)
Please choose the response below that best describes the severity of your chronic graft versus host disease symptoms over the past week .
☐ No Symptoms
Mild Symptoms
☐ Moderate Symptoms
Severe Symptoms
Very Severe Symptoms

APPENDIX G. DISEASE RISK INDEX

Disease at Diagnosis	Stage at the Time of Transplant	Disease Risk Index Group
Hodgkin lymphoma CR		Low
Hodgkin lymphoma PR		Intermediate
Hodgkin lymphoma	Advanceda	High
CLL CR		Low
CLL PR		Low
CLL	Advanceda	Intermediate
Mantle cell lymphoma CR		Low
Mantle cell lymphoma PR		Intermediate
Mantle cell lymphoma	Advanceda	High
Indolent B-cell NHL ^b CR		Low
Indolent B-cell NHL ^b PR		Low
Indolent B-cell NHLb	Advanceda	Intermediate
T-cell NHL CR		Intermediate
T-cell NHL PR		Intermediate
T-cell NHL	Advanced ^a	High
Aggressive B-cell NHL ^c CR		Intermediate
Aggressive B-cell NHL ^c PR		Intermediate
Aggressive B-cell NHL ^c	Advanceda	Very high
AML favorable cytogenetics CR		Low
AML favorable cytogenetics	Advanceda	High
AML intermediate cytogenetics CR		Intermediate
AML intermediate cytogenetics	Advanceda	High
AML adverse cytogenetics CR		High
AML adverse cytogenetics	Advanced ^a	Very high
CML chronic phase 1/2		Low
CML advanced phase		Intermediate
CML blast phase		Very high
Myeloproliferative neoplasm	Any	Intermediate
ALL CR1		Intermediate
ALL CR2		High
ALL CR3		High
ALL	Advanceda	Very high
High-risk MDS ^d adverse cytogenetics	Early ^e	High
High-risk MDS ^d intermediate cytogenetics	Early ^e	Intermediate
High-risk MDS ^d intermediate cytogenetics	Advanceda	High
High-risk MDS ^d adverse cytogenetics	Advanceda	High
Low-risk MDSf adverse cytogenetics	Earlye	Intermediate
Low-risk MDSf adverse cytogenetics	Advanceda	High
Low-risk MDSf intermediate cytogenetics	Early ^e	Intermediate
Low-risk MDSf intermediate cytogenetics	Advanced ^a	Intermediate
Burkitt lymphoma CR		High

Disease at Diagnosis	Stage at the Time of Transplant	Disease Risk Index Group
Burkitt lymphoma PR	Advanceda	Very high
Multiple myeloma CR/VGPR/PR		Intermediate
Multiple myeloma	Advanceda	High

CR = complete remission; PR = partial remission; VGPR = very good partial remission.

- ^a Advanced stage refers to induction failure or active relapse, including stable or progressive disease for NHL, Hodgkin lymphoma, and CLL.
- ^b Indolent B-cell NHL includes follicular lymphoma, marginal zone lymphoma and lymphoplasmacitic lymphoma. Small lymphocytic lymphoma is included in the CLL group.
- ^c Aggressive B-cell NHL includes diffuse large B-cell lymphoma and transformed indolent B-cell lymphoma
- ^d High-risk MDS refers to MDS with > 5% blasts (RAEB-1 and RAEB-2).
- ^e Early stage MDS includes untreated patients and patients in CR.
- $^{\rm f}$ Low-risk MDS refers to MDS \leq 5% blasts (refractory anemia with or without ringed sideroblasts and refractory cytopenia with multilineage dysplasia).

Source: Adapted from Armand et al 2014 and Armand et al 2012.

Cytogenetic groups (Armand et al 2014):

For AML:

- AML favorable cytogenetics: t(8;21), inv(16), t(15,17)
- AML adverse cytogenetics: Complex karyotype (≥ 4 abnormalities)
- AML intermediate cytogenetics: All others

For MDS and AML arising from MDS:

- MDS adverse cytogenetics: Abnormal chromosome 7 or complex karyotype (≥ 4 abnormalities)
- MDS intermediate cytogenetics: All others

APPENDIX H. PROTOCOL AMENDMENT SUMMARY OF CHANGES

Document	Date
Amendment (Version) 1:	16 AUG 2018
Amendment (Version) 2:	02 NOV 2018
Amendment (Version) 3:	30 NOV 2018
Amendment (Version) 4:	07 JUN 2019
Amendment (Version) 5:	30 AUG 2019
Amendment (Version) 6:	16 DEC 2019
Amendment (Version) 7:	03 APR 2020
Amendment (Version) 8:	30 SEP 2021

Amendment 8 (30 SEP 2021)

Overall Rationale for the Amendment: The primary purpose of this amendment is for the discontinuation of Treatment Group C in the Part 1 expansion of the study and to update risk/benefit information, the dose reduction scheme for concomitant medications, and the frequency of PFTs in GVHD follow-up.

1. Section 1, Protocol Summary (Figure 1: Study Design Schema); Section 2.3.2.3, Preliminary Results for Part 1 Expansion; Section 2.4, Benefit/Risk Assessment; Section 4.1.2, Part 1 Expansion (Table 7: Treatment Groups and Dose Levels and Schedules); Section 6.1.1, Itacitinib/Placebo (Table 9: Study Treatment Information, Part 1 Expansion)

Description of change: All relevant sections were updated to discontinue Treatment Group C (itacitinib 300 mg BID plus corticosteroids) and include preliminary data to provide the rationale for this decision.

Rationale for change: Based on emerging data and following the DMC recommendation, the sponsor decided to discontinue the itacitinib 300 mg BID study arm.

2. Section 1, Protocol Summary (Table 4: Schedule of Activities)

Description of change: Decreased frequency of FEV1% in GVHD follow-up.

Rationale for change: To remain consistent with the frequency of FEV1% assessments both on-treatment and in GVHD follow-up following Day 196 on study.

3. Section 1, Protocol Summary (Table 4: Schedule of Activities); Section 8.3.8, Laboratory Assessments (Table 20: Clinical Laboratory Analytes); Section 8.3.8.2, Serum Chemistry

Description of change: Addition of direct and indirect bilirubin for participants with high bilirubin levels.

Rationale for change: To clarify the need for bilirubin fractions (direct and indirect bilirubin) in participants with high total bilirubin to aid in cGVHD evaluation.

4. Section 2.3.2.4, Dose Modifications for Concomitant Medications (Table 5: Preliminary PK Parameters From Part 1 and Part 1 Expansion by Dose, Strong CYP3A Inhibitor Coadministration Status, and Day); Section 6.1.1.5, Criteria and Procedures for Dose Interruptions and Adjustments of Study Drug (Table 13: Itacitinib Dose Reduction for Part 1 Expansion)

Description of change: Updated the relevant sections to include the appropriate itacitinib dose reduction with concomitant use of strong CYP3A4 inhibitors and include rationale for these reductions where appropriate.

Rationale for change: To standardize the dose reduction of itacitinib with concomitant strong CYP3A4 inhibitors based upon emerging data.

5. Section 2.4 Benefit/Risk Assessment

Description of change: Updated section to include summary of recent animal studies in rats.

Rationale for change: To include additional data regarding the risk/benefit profile of the compound.

6. Section 10.4.2.2, Part 1 Expansion; Section 10.4.3, Safety Analyses

Description of change: Updated the statistics sections to clarify how the efficacy and safety analysis will be completed following the discontinuation of treatment group C.

Rationale for change: For clarification of the statistical analysis for different treatment groups in the Part 1 Expansion.

7. Appendix C, Diagnosis and Staging of Chronic GVHD (NIH Criteria)

Description of change: Addition of signs and symptoms of cGVHD.

Rationale for change: To provide NIH criteria for the first diagnosis of cGVHD in addition to staging criteria supporting eligibility assessment.

8. **Incorporation of administrative changes.** Other minor, administrative changes have been incorporated throughout the Protocol and are noted in the redline version of the amendment.

Amendment 7 (03 APR 2020)

Overall Rationale for the Amendment: The primary purpose of this amendment is for the addition of a Part 1 expansion of the study and to update inclusion criteria, dose reduction scheme for concomitant medications, and itacitinib taper.

1. Title Page; Section 1, Protocol Summary (Table 1: Objectives and Endpoints, Part 1 and Part 1 Expansion; Table 3: Key Study Design Elements; Figure 1: Study Design Schema; Table 6: Schedule of Activities); Section 2.3.1, Scientific Rationale for Study Design; Section 2.3.2.2, Rationale For Part 1 Expansion; Section 4.1, Overall Design; Section 4.1.2, Part 1 Expansion; Section 4.1.3, Part 2; Section 4.2, Overall Study Duration; Section 5.5, Replacement of Participants; Section 6.1.1, Itacitinib/Placebo; Section 6.1.1.3, Dose-Limiting Toxicity Assessment; Section 6.1.4, Determination of the Part 2 Dose; Section 6.1.2, Corticosteroids; Section 6.3.3, Prohibited Medications and Procedures; Section 8.4.1, Blood Sample Collection; Section 10.1.2, Part 1 Expansion; Section 10.3, Level of Significance; Section 10.4.1.1, Part 1 and Safety Run-In for Part 1 Expansion; Statistical Analysis; Section 10.4.2.2, Part 1 Expansion; Section 10.4.4, Pharmacokinetic Analyses; Section 10.5, Interim Analysis

Description of change: All relevant sections were updated to include the addition of a Part 1 expansion to explore additional doses and dosing schedules for itacitinib and the addition of a corticosteroids monotherapy cohort.

Rationale for change: Entire rationale is provided in Section 2.3.2.1 and is based on emerging data.

2. Section 2.3.2.3, Dose Modifications for Concomitant Medications; Section 6.1.1.3, Dose-Limiting Toxicity Assessment; Section 6.1.1.5, Criteria and Procedures for Dose Interruptions and Adjustments of Study Drug; Section 6.3.2, Restricted Medications and Procedures

Description of change: Updated the relevant sections to include the appropriate itacitinib dose reduction with concomitant use of strong CYP3A4 inhibitors and include rationale for these reductions where appropriate.

Rationale for change: To standardize the dose reduction of itacitinib with concomitant strong CYP3A4 inhibitors based upon emerging data.

3. Section 5.1, Inclusion Criteria

Description of change: Updated Inclusion Criterion 5.

Rationale for change: To ensure a more homogenous patient population with regard to bone marrow function at study entry and support a more accurate assessment of hematologic toxicity of different dosing/regimens of itacitinib.

4. Section 6.1.1.6, Tapering of Itacitinib or Placebo and Treatment Duration

Description of change: Updated the duration of treatment with itacitinib/placebo for participants achieving a CR or PR.

Rationale for change: To recommend for participants that achieved CR or PR, a treatment duration of at least 1 year, in accordance with recommendations for systemic therapy for moderate-to-severe chronic GVHD (Flowers and Martin 2015).

5. Section 7.1.1, Reasons for Discontinuation

Description of change: Revised to indicate that if during the course of the study a participant is found not to have met eligibility criteria, the participant will be discontinued unless discontinuation would result in a risk to the participant, as per the investigator's medical judgment. Removed the sponsor medical monitor from the sentence.

Rationale for change: Determination of participant discontinuation in this situation will be based on the judgment of the investigator only.

6. Section 8.3.8, Laboratory Assessments (Table 18: Clinical Laboratory Analytes)

Description of change: Updated to include cholesterol.

Rationale for change: To identify any changes in cholesterol.

7. **Incorporation of administrative changes.** Other minor, administrative changes have been incorporated throughout the Protocol and are noted in the redline version of the amendment.

Amendment 6 (16 DEC 2019)

Overall Rationale for the Amendment: The primary purpose of this amendment is specify the dose for Part 2 based on the analysis of data from Part 1 of the study, update the dose modification and interruption guidelines, and provide clarification in several areas of the Protocol.

1. Section 1, Protocol Summary (including Figure 1: Study Design Schema); Section 2.3.1, Scientific Rationale for Study Design; Section 2.3.2.1, Preliminary Results From Part 1; Section 4.1.2, Part 2; Section 6.1.1, Itacitinib/Placebo (Table 8: Study Treatment Information Part 2)

Description of change: All relevant sections were updated to include the determined dose for Part 2 and the rationale for the dose decision based on Part 1 analysis summary where applicable.

Rationale for change: To provide the dose for Part 2 of the study.

2. Section 1, Protocol Summary (Table 4: Schedule of Activities); Section 8.2.3, Hematologic Disease Relapse Monitoring; Section 8.3.8, Clinical Laboratory Analytes (Table 16: Clinical Laboratory Analytes); Section 8.8.2, Post-Treatment GVHD Follow-Up

Description of change: Updated the schedule of activities to change the frequency of cGVHD response assessment after 1 year, disease/malignancy relapse, FEV₁, several quality-of-life assessments, and correlative sample collections.

Rationale for change: To decrease the frequency of certain assessments when not necessary.

3. Section 2.3.2.2, Dose Modifications for Concomitant Medications; Section 6.3.2, Restricted Medications and Procedures

Description of change: Updated the relevant sections to include a dose reduction for concomitant medication posaconazole and include rationale from Part 1 analysis where appropriate.

Rationale for change: To add posaconazole to the list of medications requiring a dose reduction of itacitinib.

4. Section 5.1, Inclusion Criteria

Description of change: Updated inclusion criteria 2b to provide clarity of the expected corticosteroids.

Rationale for change: For clarification.

5. Section 5.2, Exclusion Criteria

Description of change: Updated exclusion criteria 3, 9, and 21 to provide clarity of the criteria. Criterion 5 was removed as it was added to exclusion criterion 9 to provide clarification.

Rationale for change: For clarification.

6. Section 6.1.1.4, Criteria and Procedures for Dose Interruptions and Adjustments of Study Drug (Table 10: Itacitinib/Placebo Dose Modification Guidelines)

Description of change: Revised guidelines for itacitinib/placebo dose modifications based on safety data from Part 1.

Rationale for change: To provide additional guidance on dose modifications.

7. Section 6.1.1.5, Tapering of Itacitinib or Placebo and Treatment Duration; Section 6.1.2.3, Corticosteroid Tapering

Description of change: Added clarification of the tapering guidelines and timelines for itacitinib, placebo, and corticosteroids.

Rationale for change: For clarification.

8. Section 6.1.2, Corticosteroids; Section 6.1.2.4, Management of Corticosteroids During cGVHD Flare

Description of change: Added clarification of the expected corticosteroids.

Rationale for change: For clarification.

9. **Incorporation of administrative changes.** Other minor, administrative changes have been incorporated throughout the Protocol and are noted in the redline version of the amendment.

Amendment 5 (30 AUG 2019)

Overall Rationale for the Amendment: The primary purpose of this amendment is to ensure consistency between sections of the Protocol describing the reasons for discontinuation in response to VHP request.

1. Section 7.1.1, Reasons for Discontinuation

Description of change: Clarified that a participant must be withdrawn from study treatment if "additional systemic therapy is considered due to lack of clinical benefit from study treatment."

Rationale for change: To ensure consistency between Section 6.1.1.5 and Section 7.1.1 regarding discontinuation of treatment in the case of a lack of clinical benefit.

2. **Incorporation of administrative changes.** Other minor, administrative changes have been incorporated throughout the Protocol and are noted in the redline version of the amendment.

Amendment 4 (07 JUN 2019)

Overall Rationale for the Amendment: The primary purpose of this amendment is to update and clarify exclusion criteria, definition for treatment failure, DLT criteria, treatment of overdose, and maximum duration of study treatment, as well as respond to health authorities.

1. Section 1, Protocol Summary (Table 3: Key Study Design Elements; Table 4: Schedule of Activities); Section 4.1.1, Part 1; Section 4.1.2, Part 2; Section 8.8.2, Post-Treatment GVHD Follow-Up

Description of change: Revised to clearly define treatment failure in the context of this protocol and provide clarification on the post-treatment follow-up portion of the study.

Rationale for change: To provide clarification to the definition of treatment failure and ensure consistency with Table 5 (Objectives and Endpoints, Part 1).

2. Section 1, Protocol Summary (Table 3: Key Study Design Elements); Section 4.1.1, Part 1; Section 4.1.2, Part 2; Section 4.2, Overall Study Duration

Description of change: Updated the estimated duration of study participation.

Rationale for change: For clarification.

3. Section 1, Protocol Summary (Table 2: Objectives and Endpoints, Part 2; Table 4: Schedule of Activities); Section 3, Objectives and Endpoints (Table 6: Objectives and Endpoints, Part 2); Section 8.2.4, Patient-Reported Outcomes; Section 10.4.2.2, Part 2; Appendix E, Patient Global Impression of Change and Patient Global Impression of Severity

Description of change: Added the PGIC and PGIS questionnaires to the patient-reported outcomes and updated all relevant sections.

Rationale for change: To collect and provide additional data for patient-reported changes.

4. Section 5.2, Exclusion Criteria

Description of change: Updated exclusion criteria 1, 4, and 10 to clarify the criteria. Updated exclusion criterion 11 to provide clarity and differentiate between the conflicting time frame in exclusion criterion 3, which is specific to the use of corticosteroids for the purpose of cGVHD.

Rationale for change: Clarification to address frequently asked questions.

5. Section 6.1.1.3, Dose-Limiting Toxicity Assessment and Determination of Part 2 Dose (Table 9: Definitions of Dose-Limiting Toxicity)

Description of change: Added criteria that transient abnormal laboratory values without associated clinically significant signs and symptoms and not leading to hospitalization will not be considered as DLTs.

Rationale for change: To provide guidance and clarification for events qualifying as a DLT.

6. Section 6.1.1.4, Criteria and Procedures for Dose Interruptions and Adjustments of Study Drug

Description of change: Section updated to include additional details and guidance regarding dose reductions and modifications.

Rationale for change: For clarification.

7. Section 6.1.1.5, Tapering of Itacitinib or Placebo and Treatment Duration

Description of change: Section updated to include the maximum duration for study treatment and examples of the taper.

Rationale for change: For clarification.

8. Section 6.3.3, Prohibited Medications and Procedures

Description of change: Section updated to include clarification regarding maintenance therapy for primary hematologic disease while on study.

Rationale for change: For clarification.

9. Section 8.1.1, Informed Consent Process

Description of change: Section updated to include guidance specific to Germany regarding authorized legal representation.

Rationale for change: Feedback from VHP.

10. Section 8.1.5.1, Demographics and General Medical History

Description of change: Removed language stating that the collection of medical history will include "date of birth, race, ethnicity, medical and surgical history, and current illnesses. Medical history will include relevant medical or surgical treatment details that are considered to be clinically significant by the investigator."

Rationale for change: To correct an error, since date of birth will not be collected and for consistency with other itacitinib protocols.

11. Section 8.1.5.2, Disease Characteristics and Treatment History

Description of change: Updated to include details about disease-targeted medical and treatment history.

Rationale for change: To provide more detail on information that should be collected.

12. Section 8.3.5, Infection Monitoring

Description of change: Removed testing for herpes simplex virus, human T-cell lymphotropic virus 1/2, hepatitis A, and IgG/IgM toxoplasmosis from routine infection monitoring.

